## **4. REGISTRATION PROCEDURES**

### **4.1 General Guidelines for DF/HCC and DF/PCC Institutions**

Institutions will register eligible participants with the DF/HCC Office of Data Quality (ODQ) central registration system. Registrations must occur prior to the initiation of protocol therapy. Any participant not registered to the protocol before protocol therapy begins will be considered ineligible and registration will be denied.

An investigator will confirm eligibility criteria and a member of the study team will complete the ODQ protocol-specific eligibility checklist.

Following registration, participants may begin protocol therapy. Issues that would cause treatment delays should be discussed with the Overall Principal Investigator (PI). If a participant does not receive protocol therapy following registration, the participant's registration on the study must be canceled. Notify the ODQ Registrar of registration cancellations as soon as possible.

#### 4.2 Registration Process for DF/HCC and DF/PCC Institutions

The ODQ registration staff is accessible on Monday through Friday, from 8:00 AM to 5:00 PM Eastern Standard Time. The registration procedures are as follows:

- Obtain written informed consent from the participant prior to the performance of any protocol specific procedures or assessments.
- Complete the ODQ protocol-specific eligibility checklist using the eligibility assessment documented in the participant's medical record and/or research chart. **To be eligible for registration to the protocol, the participant must meet all inclusion and exclusion criterion as described in the protocol and reflected on the eligibility checklist.**  
Reminder: Confirm eligibility for ancillary studies at the same time as eligibility for a treatment protocol. Registration to both treatment and ancillary protocols will not be completed if eligibility requirements are not met for all studies.
- Fax the eligibility checklist(s) and all pages of the consent form(s) to the ODQ at [contact]. For Phase I protocols, attach participant dose level assignment confirmation from the sponsor.
- The ODQ Registrar will (a) review the eligibility checklist, (b) register the participant on the protocol, and (c) randomize the participant when applicable.
- An email confirmation of the registration and/or randomization will be sent to the site's oncology clinical trials pharmacy.

#### 4.3 External Site Registration process

- The external site obtains informed consent and screens the participant for eligibility.
- An appropriately delegated and qualified individual at the external site signs off as screening staff on the eligibility checklist.
- The external site sends the completed eligibility checklist and signed informed consent document to the DF/HCC coordinating center.
- When required per [REGIST-104](#), an enrollment monitor at the coordinating center must verify participant eligibility and sign the eligibility checklist.

- The DF/HCC coordinating center is responsible for registering the subject in OnCore (de-centralized), or sending the registration packet to ODQ (centralized).
- The DF/HCC coordinating center will forward registration confirmation to the external site.
- The external site must notify the coordinating center of subject status changes (off treatment, off study).
- The DF/HCC coordinating center is responsible for updating the subject status in OnCore (de-centralized), or notifying ODQ (centralized).

## **5. TREATMENT AND/OR IMAGING PLAN**

### **5.1 Treatment Regimen**

Atorvastatin (or placebo) will be at a dose of 40 mg once a day. If the participant develops muscle pain, myalgia, then the study drug dose can be reduced to 20 mg once a day or placebo.

Atorvastatin (or placebo) will be taken nightly. Treatment will be administered on an outpatient basis. Reported adverse events and potential risks are described in Section 7.

### **5.2 Pre-Treatment Criteria**

If required (no recent measurement of < 1 month), measurement of CBC, potassium, renal function and liver function will be obtained. Lab values will be used from oncology providers if needed.

### **5.3 Lab Values**

Lab values for follow up visits will be taken from subjects oncology team throughout study calendar until patient is off study.

### **5.4 Agent Administration**

The drug is taken by mouth, once a day (evening) for the entire study. The study medication should be swallowed. The drugs can be taken with food and with any other medications. Any unused study drug will be brought back for the next study visit. The medications can be stored at room temperature for the duration of the study. If the medication is vomited, it can be taken again within the same day.

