### **3.2 Exclusion Criteria:**

- Statin use or Statin use is indicated based on guidelines
- Pregnancy or breastfeeding
- Unable to provide informed consent
- Unexplained persistent elevation of transaminases (>3 times upper limits of normal)
- Concomitant use of oral cyclosporine
- Contraindication to a CMR (metallic object, severe claustrophobia, pacemaker, vascular clip)

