### **5.5 General Concomitant Medication and Supportive Care Guidelines**

Atorvastatin is widely used in clinical care and is not an investigational agent.

Patients will be followed throughout the study by a nurse practitioner under the supervision of a cardiologist.

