## **5.6 Criteria for Taking a Participant Off Protocol Therapy**

Duration of therapy will be of 12 months. In the absence of treatment delays due to adverse event(s), treatment may continue for 12 months or until one of the following criteria applies:

- Intercurrent illness that prevents further administration of treatment
- Unacceptable adverse event(s)
- Participant demonstrates an inability or unwillingness to comply with the oral medication regimen and/or documentation requirements
- Participant decides to withdraw from the protocol therapy
- General or specific changes in the participant's condition render the participant unacceptable for further treatment in the judgment of the treating investigator

Participants will be removed from the protocol therapy when any of these criteria apply. The reason for removal from protocol therapy, and the date the participant was removed, must be documented in the case report form (CRF). Alternative care options will be discussed with the participant.

A ODQ Treatment Ended/Off Study Form will be filled out when a participant is removed from protocol therapy. This form can be found on the ODQ website or obtained from the ODQ registration staff.

Emergency unblinding will occur in case of unacceptable adverse event that may be caused by atorvastatin, i.e. severe allergic reaction or rhabdomyolysis.

In the event of unusual or life-threatening complications, treating investigators must immediately notify the Overall PI, [name] at [name] (page) or [name] (cell phone).

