## 6. DOSING DELAYS/DOSE MODIFICATIONS

Treatment will be temporarily suspended if the liver function tests elevate by more than 3 times normal. If it is determined that the elevation in liver function tests are due to another cause, the treatment will be reinstated provided the liver function tests return to normal. The patients with side effects will not be excluded from the protocol. If the participant develops muscle pain, myalgia, then the study drug dose can be reduced to 20 mg once a day or placebo. If the symptoms do not respond to this within 1 week then the study drug is stopped. This is what happens in clinical practice.

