### 8.1 IND Agent #1: Atorvastatin

#### 8.1.1 Description

Atorvastatin is a member of the drug class known as statins, which are used primarily as a lipid-lowering agent and for prevention of events associated with cardiovascular disease. Like all statins, atorvastatin works by inhibiting HMG-CoA reductase, an enzyme found in liver tissue that plays a key role in production of cholesterol in the body.

Atorvastatin undergoes rapid absorption when taken orally, with an approximate time to maximum plasma concentration (Tmax) of 1–2 h. The absolute bioavailability of the drug is about 14%, but the systemic availability for HMG-CoA reductase activity is approximately 30%. Atorvastatin undergoes high intestinal clearance and first-pass metabolism, which is the main cause for the low systemic availability. Administration of atorvastatin with food produces a 25% reduction in Cmax (rate of absorption) and a 9% reduction in AUC (extent of absorption), although food does not affect the plasma LDL-C-lowering efficacy of atorvastatin. Evening dose administration is known to reduce the Cmax and AUC by 30% each. However, time of administration does not affect the plasma LDL-C-lowering efficacy of atorvastatin.

It is highly protein bound (≥98%), and studies have shown it is likely secreted into human breast milk.

Atorvastatin metabolism is primarily through cytochrome P450 3A4 hydroxylation to form active ortho- and parahydroxylated metabolites, as well as various beta-oxidation metabolites. As a substrate for the CYP3A4 isozyme, it has shown susceptibility to inhibitors and inducers of CYP3A4 to produce increased or decreased plasma concentrations, respectively. This interaction was tested in vitro with concurrent administration of erythromycin, a known CYP3A4 isozyme

inhibitor, which resulted in increased plasma concentrations of atorvastatin. It is also an inhibitor of cytochrome 3A4.

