## 10. STUDY CALENDAR

After consent is obtained, patients will undergo a baseline visit including a questionnaire, vital sign measurements, an MRI, echocardiogram and blood sampling. A pregnancy test (urine beta-HCG) will be performed as appropriate. A second visit similar to the first one will be scheduled after 3 cycles of chemotherapy (approx 3 months). The final study visit will be at 12 months where subjects will undergo an echo, MRI and blood sampling.

An additional visit for the sub-group in the MRI mechanistic sub-study will occur at 6 months where this sub-group will undergo an additional cardiac MRI.

We will do a balanced randomization with blocks of 2 patients for each cancer site.

Baseline evaluations are to be conducted within 1 week prior to start of anthracyclines therapy. Assessments must be performed prior to administration of any study agent. Study assessments and agents should be administered within  $\pm 7$  days of the protocol-specified date, unless otherwise noted.

	Pre-Study	Study Drug	1 month	2 months	3 months	6 months	12 months	24 months
Atorvastatin/placebo		X-----X						
Informed consent	X							
Demographics	X							
Medical history	X							
Perceived Stress Scale	X				X	X	X	
Physical exam	X				X		X	
Vital signs	X		X		X		X	

Height	X							
Weight	X					X	X	
Phone call: Adverse and clinical events	X		X	X	X	X	X	X
LFTS	X		X		X			
Lipids/Blood biomarkers	X				X		X	
B-HCG	X					X	X	
Echocardiogram	X				X		X	
MRI	X					X	X	
Pill count (Monthly)								

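### The protocol excludes oral cyclosporine at entry but gives no rule if it is started on study, and Section 5.4 as worded permits any co-medication

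*Protocol*

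**What the plan says.** The relevant statements are all in the protocol. The SAP does not address co-medication.

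- **Section 5.4 (Agent Administration):** "The drugs can be taken with food and with any other medications". No exception follows. The neighbouring sentences deal with swallowing the capsule, returning unused drug, storage and vomited doses.
- **Section 5.5 (General Concomitant Medication and Supportive Care Guidelines):** two sentences. The first is "Atorvastatin is widely used in clinical care and is not an investigational agent". The second places follow-up with a nurse practitioner supervised by a cardiologist. No drug is prohibited, restricted or cautioned.
- **Section 3.2 (Exclusion Criteria):** "Concomitant use of oral cyclosporine".
- **Section 8.1.1 (Description):** of atorvastatin as a CYP3A4 substrate, "it has shown susceptibility to inhibitors and inducers of CYP3A4 to produce increased or decreased plasma concentrations, respectively". The one example, erythromycin, is described as tested in vitro, and no size of effect is given.
- **Section 6 (Dosing Delays/Dose Modifications):** "Treatment will be temporarily suspended if the liver function tests elevate by more than 3 times normal". Myalgia allows a reduction to 20 mg, and the drug is stopped if symptoms do not respond within a week.
- **Section 5.6 (Criteria for Taking a Participant Off Protocol Therapy):** general grounds, including "Intercurrent illness that prevents further administration of treatment" and the treating investigator's judgment after a change in the participant's condition. Starting an excluded drug is not listed.

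**The concern.** The protocol treats one co-medication as serious enough to bar enrolment and recognizes a wider metabolic interaction. It then gives an unqualified permission for the 12 months of dosing. A site that wants to know whether a newly prescribed drug is compatible with study drug finds that permission in 5.4 and nothing to the contrary in 5.5.

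Two things are at stake. The first is participant safety: someone whose cyclosporine use would have kept them out of the trial may go on taking 40 mg of atorvastatin alongside it. The second is consistency: with no stated action, one site may hold the drug, another reduce it, another stop it for good and another carry on. The reliability of the primary comparison is not in question.

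**Working it through.** No arithmetic applies. The plan states no figure on this point, and none can be derived from it. The check is to see whether any section carries the entry exclusion into the treatment period or states an action.

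1. **Does 3.2 reach past entry?** The word for concurrent use could be meant to apply throughout. However, it sits only in the eligibility list, which Section 4.2 applies at registration. No later section repeats it.
2. **Does 5.4 carve out an exception?** No. Its permission covers every other medicine.
3. **Does 5.5 correct 5.4?** No. Neither of its two sentences limits any drug.
4. **Does Section 6 act when the drug is started?** No. Its two triggers are liver tests above three times normal and muscle symptoms. Both act after an effect has appeared.
5. **Does 5.6 act when the drug is started?** Only by discretion. An investigator may judge the participant unsuitable for further treatment, but nothing names the drug or directs a hold.
6. **Does 8.1.1 give an instruction?** No. It describes the interaction and gives no dosing advice.
7. **Would the start of cyclosporine be noticed?** Possibly. The study calendar in Section 10 has no visible co-medication row. The case report form and questionnaire are not in the documents, so co-medications may be recorded there. Adverse- and clinical-event calls are scheduled at months 1, 2, 3, 6 and 12 during treatment.
8. **What monitoring remains?** Study liver tests fall at baseline, month 1 and month 3, which matches the statement in Section 7.1.1 that most liver abnormalities occur in the first three months. For laboratory values generally, Section 5.3 says: "Lab values for follow up visits will be taken from subjects oncology team throughout study calendar until patient is off study". Section 12.2 adds toxicity review by the safety monitoring committee up to four times a year, or more often if required.

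Steps 1 to 6 show that nothing on the page forbids continuing 40 mg and nothing requires it. Steps 7 and 8 show that the exposure would not go unwatched.

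**Size.** An expected number of events would need the proportion of participants who start oral cyclosporine and the factor by which that raises the risk of muscle or liver toxicity. The documents give neither. The toxicity rates in Sections 2.2 and 7.1.1 describe statin users in general and cannot supply either quantity. Any count would rest on assumptions alone, so none is given.

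**The case against.** The strongest reply is that the sentence in 5.4 is about handling. Read among its neighbours, it most naturally says that the capsule need not be separated from meals or other pills. A specific exclusion for concurrent cyclosporine would then prevail over a general remark on swallowing capsules. Clinical judgment is also in place: a cardiologist oversees follow-up, 5.6 lets the investigator stop treatment, and laboratory tests, calls and committee review continue. Under Section 13.1 the site's research pharmacy knows the assignment, although the protocol does not say that it screens for interactions. Finally, consent pages were removed from the text, and the eligibility checklist and case report form are not shown, so participants or sites may receive advice on other medicines there.

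Most of this stands, and it is why the point is minor. It does not remove the gap. The handling reading is plausible but is not what the words say, and 5.5, where a reader would look for the limit, is silent. Judgment and monitoring reduce the risk without telling a site what to do on the day the excluded drug is prescribed.

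A reader might infer more than the documents support:

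- **That the protocol directs sites to continue 40 mg with cyclosporine.** It does not. Continuation is permitted by the wording, and 5.6 allows stopping.
- **That a number of participants can be expected to come to harm.** No rate of use and no size of interaction is given.
- **That a full list of prohibited CYP3A4 inhibitors is missing.** Section 8.1.1 is descriptive and gives no effect size. Which further drugs to restrict during lymphoma treatment is a clinical choice that these documents do not settle. Oral cyclosporine is the one drug the protocol itself has already ruled out.

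**Conclusion.** The point holds as a minor participant-safety correction. The wording of 5.4 conflicts with the protocol's own exclusion and interaction statement, and 5.5 does not resolve the conflict. This is a stated permission at odds with the protocol's safety reasoning, which goes further than an absence of detail.

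The size cannot be expressed as events. Nothing in the sample-size calculation, the significance level or the primary analysis depends on it.

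The conclusion rests on two assumptions: that 5.4 is read as worded, and that no document outside the protocol and SAP already tells sites what to do if oral cyclosporine is started. If such an instruction exists, only the wording of 5.4 needs attention.

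**What to change.** 1. **Section 5.4.** Replace the part of the sentence after the mention of food with: *and need not be taken separately from other permitted medicines (see 5.5).*
2. **Section 5.5.** Add: *Oral cyclosporine is not permitted while on study drug. If it is started, study drug is held while it is given, regardless of arm and without unblinding; follow-up and the 12-month CMR continue and analysis stays intent-to-treat.* This is the same kind of temporary suspension that Section 6 already uses for liver tests, and it leaves the intent-to-treat rule in Section 13.6.2 untouched.
3. **Existing contacts.** At the calls already scheduled during treatment, ask one closed question: has oral cyclosporine been started? An open question about interacting drugs should not be added, because without a list and an action for each drug it would recreate the gap.

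The cost is two wording changes and one question, with no new visits, tests or participants. The downside is that a few participants may have study drug interrupted, which would slightly lower exposure in the statin arm under intent-to-treat.

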### **5.5 General Concomitant Medication and Supportive Care Guidelines**

Atorvastatin is widely used in clinical care and is not an investigational agent.

Patients will be followed throughout the study by a nurse practitioner under the supervision of a cardiologist.

## **5.6 Criteria for Taking a Participant Off Protocol Therapy**

Duration of therapy will be of 12 months. In the absence of treatment delays due to adverse event(s), treatment may continue for 12 months or until one of the following criteria applies:

- Intercurrent illness that prevents further administration of treatment
- Unacceptable adverse event(s)
- Participant demonstrates an inability or unwillingness to comply with the oral medication regimen and/or documentation requirements
- Participant decides to withdraw from the protocol therapy
- General or specific changes in the participant's condition render the participant unacceptable for further treatment in the judgment of the treating investigator

Participants will be removed from the protocol therapy when any of these criteria apply. The reason for removal from protocol therapy, and the date the participant was removed, must be documented in the case report form (CRF). Alternative care options will be discussed with the participant.

A ODQ Treatment Ended/Off Study Form will be filled out when a participant is removed from protocol therapy. This form can be found on the ODQ website or obtained from the ODQ registration staff.

Emergency unblinding will occur in case of unacceptable adverse event that may be caused by atorvastatin, i.e. severe allergic reaction or rhabdomyolysis.

In the event of unusual or life-threatening complications, treating investigators must immediately notify the Overall PI, [name] at [name] (page) or [name] (cell phone).

## **5.7 Duration of Follow Up**

This study lasts for 12 months after start of the treatment. Participants removed from protocol therapy for unacceptable adverse event(s) will be followed until resolution or stabilization of the adverse event.

## **5.8 Criteria for Taking a Participant Off Study**

Participants will be removed from study when any of the following criteria apply:

- Lost to follow-up
- Withdrawal of consent for data submission
- Death

The reason for taking a participant off study, and the date the participant was removed, must be documented in the case report form (CRF).

A ODQ Treatment Ended/Off Study Form will be filled out when a participant comes off study. This form can be found on the ODQ website or obtained from the ODQ registration staff.

## 6. DOSING DELAYS/DOSE MODIFICATIONS

Treatment will be temporarily suspended if the liver function tests elevate by more than 3 times normal. If it is determined that the elevation in liver function tests are due to another cause, the treatment will be reinstated provided the liver function tests return to normal. The patients with side effects will not be excluded from the protocol. If the participant develops muscle pain, myalgia, then the study drug dose can be reduced to 20 mg once a day or placebo. If the symptoms do not respond to this within 1 week then the study drug is stopped. This is what happens in clinical practice.

## 7. ADVERSE EVENTS: LIST AND REPORTING REQUIREMENTS

Adverse event (AE) monitoring and reporting is a routine part of every clinical trial. The following list of reported and/or potential AEs (Section 7.1) and the characteristics of an observed AE (Section 7.2) will determine whether the event requires expedited reporting **in addition** to routine reporting.

### 7.1.1 Adverse Event List(s) for Commercial Agent(s)

**Atorvastatin:** Subjects will be randomized to either placebo or atorvastatin as part of the proposed protocol.

*Risk of statin therapy:* Subjects will be randomized to either placebo or atorvastatin as part of the proposed protocol. The reported risks of atorvastatin therapy include statin myopathy, rhabdomyolysis, renal failure as a result of rhabdomyolysis, and hepatotoxicity.

**Muscle toxicity:** In statin clinical trials, the reported incidence of myopathy is low (0.1%) and data from a large meta-analysis (with 246,955 patients) of patients taking statins has been reported the incidence of myopathy to be similar to control. In another compilation of randomized controlled statin trials revealed that among 83,858 patients randomly assigned to receive either statin treatment or placebo, there were 49 cases of myositis and 7 cases of rhabdomyolysis in the statin groups, compared with 44 cases of myositis and 5 cases of rhabdomyolysis in the placebo groups. The risk of skeletal muscle effects such as myopathy and rhabdomyolysis increase in a dose-dependent manner with advanced age ( $\geq 65$ ) and renal impairment. However, patients with renal failure will be excluded due to the administration of CMR contrast.

**Hepatotoxicity:** Based on guidelines, a modest elevation in transaminases to less than 3 times the upper limits of normal will not be considered a contra-indication to inclusion in the study. The incidence of elevated liver biochemical tests is increased to 1% of patients on statins. The majority of liver abnormalities occur within the first 3 months of therapy. Fulminant hepatic failure from statin therapy, without the presence of rhabdomyolysis and renal failure, is rare.

